7.4.1 Baseline Data

After 10 participants are randomly assigned to each stimulation order, an analysis of demographic data (age, education, gender, symptom severity) will address any initial differences in baseline characteristics of the two samples. If there is a systematic difference, randomization will be temporarily suspended to assign patients to one or other of the two groups in order to re-balance the initial baseline characteristics of the two groups. [Independent samples t-tests for continuous variables and Chi-square for categorical variables]

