3.1 General Design

TMS will be administered to either the fMRI-guided target or DLPFC in a randomized, single-blind design. 40 patients diagnosed with Post-Traumatic Stress Disorder (PTSD) or trauma induced Major Depressive Disorder (MDD) and symptoms of depression, as determined by meeting the DSM criteria for PTSD or MDD as a primary diagnosis and scoring ≥10 on the PHQ-9, will be recruited for this study. They will be otherwise healthy adults, aged 18-60, with PTSD or trauma induced MDD as primary diagnosis and without current diagnoses of significant, problematic substance use disorders or with present or past diagnoses of psychosis or bipolar illness. All subjects will receive active TMS, so there is no placebo or sham condition. However, the patients will be blinded as to whether their site of stimulation is based on the clinical standardized targeting method or our novel fMRI-guided targeting method. TMS is administered to one of these two sites over a two-week period, and then TMS will be administered to the other site over a subsequent two-week period following a three week wash out period. All subjects will receive TMS to both sites as a part of the study, but the order is randomized and counterbalanced. All participants will be recruited through the community via study advertisements and through the University of Pennsylvania and the VA. Subjects can express interest by contacting the study staff; in most cases, this will serve as the primary method for acquiring contact information. Physician referrals and the use of the Penn Data Analytics Center will also be incorporated as recruitment methods. Section 4.3 further elucidates all recruitment methods. Prior to any study visits, all subjects will be screened in a telephone interview with a trained member of the study staff or via a self-report screening survey. The first study session will consist of a consenting and extended screening visit. The information collected in this initial visit will determine if the subject meets all inclusion criteria. We will also demonstrate TMS to ensure the subject is comfortable with all study procedures. At the second study session, participants will undergo an MRI procedure for 60 minutes. This will be used to generate the TMS targets for the study. Subjects will then return every weekday (5 days per week, minimum of 4 days per week) over two weeks to receive the TMS treatment (10 sessions). These visits will last approximately 60 minutes each. The daily administration of TMS is a necessary component of the study, as it is consistent with the standard operating procedure for FDAapproved clinical TMS. During the 2 weeks of TMS treatment, subjects will undergo the many of the same clinical assessments used during the screening and baseline visits, in order to examine changes in symptoms. Subjects will then spend 3 weeks away from the study team; during the break, there will be two phone/survey visits used as a safety assessment. After this break, subjects will then return every weekday (5 days per week, minimum of 4 days per week) over two weeks to receive the TMS treatment (10 sessions) to the other site examined in the study. Upon completion of the study, scheduled phone and survey visits will take place every 4 weeks (+/-7 days) over the subsequent 6-month period to monitor continued stability of clinical improvement and/or remaining clinical symptoms. Overall, this study consists of 1 consent/screening visit, 1 MRI scan, 20 total visits for TMS treatment, and 8 phone visits.

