3.1.2 Study Intervention Phase

Allocation to Interventional Group - Subjects will be randomly assigned to receive TMS at either the fMRIguided target or the DLPFC during this study. This is a single-blind study, so the researchers will know the site of administration for each subject, whereas subjects will remain blinded. The research team will be responsible for randomizing subjects using a computer-based randomization algorithm.

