4.5 Total Number of Subjects and Sites

It is expected that approximately 80 subjects will be consented/enrolled at Penn in order to produce 40 evaluable subjects in total (due to missing data, drop out, etc.).

4.6 Vulnerable Populations:

No children, pregnant women, fetuses, neonates, or prisoners are included in this research study.

5 Study Intervention (Study drug, device, biologic, vaccine, food etc.)

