Visits 2-11 are the first set of TMS treatment visits; each visit will take approximately 1 ½ to complete. If participants have time limitations, or during the COVID-19 pandemic, we may provide the option to complete the clinical assessments remotely (by phone/ sending the surveys) and we will make a note in their records. Brain data from the MRI scan (stimulation target in individualized brain space) will be calibrated with the skin and scalp using a Polaris Vicra camera (Brainsight neuronavigation) to allow marking of the stimulation sites. In addition, subjects will be evaluated to determine their motor threshold, or the amount of stimulation at the motor cortex needed to create an involuntary thumb twitch. This preparation time is expected to take approximately 30 minutes. Then, the TMS devices will be used to administer theta-burst stimulation (. TBS will be administered twice per session, with approximately a 20 minute break between each round of TMS. Participants will complete a short clinical assessment before and after each TBS session.

During the break between TMS rounds, participants will either complete a working memory task or watch a peaceful video;. These tasks are being added to the study protocol in order to activate brain areas through which the TMS treatments are expected to enhance relaxed mood (nature videos) or increase cognitive control (nback working memory task). Randomization will be by random number generator with eventual matching by demographics (age, race, gender) to balance the groups later in the study, as necessary.

During TMS, subjects will be asked to sit still for approximately seven minutes at a time when TBS is administered. The total number of stimulations in each TBS block is 1200 stimulations, for a total of 2400 stimulations. We approximate that the additional single pulses to determine motor threshold will not exceed 100 additional pulses. At the end of each TBS session, participants will complete additional clinical assessments. If participants have time limitations, we may provide the option to complete the clinical assessments remotely (by phone/ sending the surveys), and we will make a note in their records. TBS sessions are expected to take approximately 1 ½ hours, except for Visit #11 and visit #23 which will involve CONFIDENTIAL

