7.4 Statistical Methods

The primary analysis will be a Site x Time ANOVA on the Hamilton Depression rating scale comparing pretreatment to symptoms immediately following each round of stimulation. This test will be augmented by a Site x Time ANOVA for pre-treatment compared with the 6 month timepoint to explore the degree of maintenance of treatment benefits.

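### A chance baseline imbalance after 10 patients per order would temporarily replace randomised treatment order with assignment by patient characteristics

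*Combined protocol and SAP*

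**What the plan says.** Section 3.1 (General Design) describes a crossover: "All subjects will receive TMS to both sites as a part of the study, but the order is randomized and counterbalanced". Section 5.4 repeats that the order is randomised and counterbalanced. Section 3.1.2 says who does it: "The research team will be responsible for randomizing subjects using a computer-based randomization algorithm". It adds that researchers know each subject's site.

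Section 7.4.1 sets a check. "After 10 participants are randomly assigned to each stimulation order", age, education, gender and symptom severity are compared between the two orders. If a systematic difference is found, "randomization will be temporarily suspended to assign patients to one or other of the two groups in order to re-balance the initial baseline characteristics". A bracketed note lists "Independent samples t-tests for continuous variables and Chi-square for categorical variables".

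The section does not define *systematic*, give a significance level, say who assigns, limit how many patients are assigned this way, say when randomisation resumes, or say how the analysis treats these patients.

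**The concern.** If the first patients were properly randomised, chance is the only source of a difference between the orders, so there is nothing systematic to detect. A test of that difference can only flag the occasional unlucky draw. The response is to stop randomising for a time and choose each patient's order from that patient's baseline profile. Sections 3.1 and 5.4 would then not describe part of the sample.

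Balance is a fair aim in a trial of about 40 patients, but it can be pursued without interrupting randomisation. At stake are the comparisons for which random order is the safeguard:

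- Patients who leave after the first treatment set. For them order and site are the same thing, and section 7.5 lets completed time-points be used in some analyses.
- The 6-month comparison in section 7.4.
- Protection against period and carry-over effects. The section 7.4 ANOVA names no term for either, so random order is the main defence.

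**Working it through.** **Inputs from the plan.** Check at 10 per order; four variables; t-tests and chi-square (all section 7.4.1). Target of 40 evaluable patients from about 80 enrolled (section 4.5). The plan gives no figure for how often the rule would act, so there is none to reproduce; the 6 patients in section 7.3 concern power and do not enter.

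**Assumptions.** The trigger is at least one significant test at two-sided 0.05. This is inferred from the bracketed tests, not stated. Age, education and severity are normal with pairwise correlation 0 to 0.5. One gender makes up 50% to 80% of patients. Chi-square is taken with and without continuity correction.

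**1. How often the rule fires by chance.** With four independent tests: 1 - 0.95^4 = 0.185. By simulation of sound 10 versus 10 samples:

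| Per-test level | Chance of at least one significant test |
|---|---|
| 0.01 | 3-4% |
| 0.05 | about 13-18% |
| 0.10 | 27-36% |

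(The 0.01 and 0.10 rows use gender shares of 50% and 65% only.)

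**2. What size of difference a t-test needs.** The critical observed difference is 2.101 x sqrt(2/10) = 0.94 SD. Smaller imbalances, which may still matter, leave the rule idle.

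**3. How many patients remain to be assigned at the check.**

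- Blocked allocation, all evaluable: 40 - 20 = 20.
- Simple randomisation, all evaluable: reaching 10 in both orders takes more than 20 patients in about 82% of trials (mean 23.5, 90th percentile 28). That leaves 40 - 23.5 = 16.5 on average and 40 - 28 = 12 at the 90th percentile, so typically 12-17.
- Blocked allocation, only half of the first 20 evaluable: 40 - 10 = 30. This is an upper illustration, since the planned 40-of-80 yield also counts screen failures (section 7).

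**4. How many might be assigned non-randomly once triggered.** The plan gives no end point. As an illustration, each next patient is given the order that most reduces the summed squared standardised differences, in samples that triggered at 0.05:

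| Stop when | Median patients (90th percentile) |
|---|---|
| no test has p < 0.05 | 2 (6) |
| all differences < 0.5 SD | 7 (11) |
| all differences < 0.25 SD | 13 (18) |

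**5. What the alternatives achieve at 20 patients.** Minimisation on four two-level factors, with the preferred order given with probability 0.8, leaves about a 2-4% chance of any significant difference at 0.05. Blocks stratified by severity alone leave about 7-14% for age, education or gender: 10-14% at zero correlation and about 7-10% at correlation 0.5.

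**6. How guessable the alternatives are over 40 patients.** These rates are for someone who knows the past allocations and, where relevant, the patient characteristics or block sizes. Best-guess accuracy is about 75% under minimisation at 0.8, 70% with fixed blocks of 4 in two strata, and 67% with mixed blocks of 4, 6 and 8. With fixed blocks of 4, about 31% of allocations are certain; with mixed blocks of known size, 22%. Under minimisation at 0.8, none is certain.

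**The case against.** The strongest reply is that the practical effect is small. The suspension is conditional and temporary, and in a crossover most differences between order groups cancel from the within-patient site contrast. Multiplying the trigger rate by the median numbers above gives 0.13 x 2 to 0.18 x 2, about 0.3 non-randomly assigned patients per trial. At the strictest stopping point it is 0.13 x 13 to 0.18 x 13, about 2. These products use medians and are rough, and no bias in an estimate has been computed. All of this stands, and it limits the size of the point.

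Four stronger readings are tempting, and the documents do not support them:

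- *The primary comparison is invalid.* It is not; every completer contributes both sites.
- *The rule ruins the 6-month analysis.* Section 7.4 says "This test will be augmented by a Site x Time ANOVA for pre-treatment compared with the 6 month timepoint" and gives the purpose as exploratory. By then completers have had both sites, so a site effect could not be separated from order even under perfect randomisation. That is a different problem.
- *Unmasked staff would choose orders by hand.* Section 7.4.1 does not say who assigns or how, and the assignment could be algorithmic. What can be said is that no random element is described.
- *Section 6.2.2 confirms a wider practice.* It mentions "eventual matching by demographics (age, race, gender) to balance the groups later in the study, as necessary", but directly after describing the working-memory task and video used in the break. The natural reading is randomisation of that task, so it is not counted here.

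It can also be said that minimisation makes order depend on characteristics too. That is true. The difference is that it keeps a random element throughout and is fixed in advance.

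**Conclusion.** The concern holds in a limited form. Section 7.4.1 allows randomised order to be replaced for a time by assignment on baseline characteristics, in response to what can only be a chance difference, under a rule whose threshold, operator and end point are undefined. On the assumed 0.05 trigger, this would happen in about 13-18% of trials with sound randomisation.

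The pool still to be assigned at the check is about 20 of 40 evaluable patients if allocation is blocked and all are evaluable. It is typically 12-17 under simple randomisation, and larger if some early patients prove not evaluable. Twenty should therefore not be read as a minimum.

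The within-patient site contrast is little affected. The harm is confined to comparisons that depend on order. The change is still worth making, because a better method costs almost nothing.

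**What to change.** 1. Delete the suspension rule in section 7.4.1.
2. From the first patient, have the computer algorithm in section 3.1.2 use minimisation with a random element (for example, probability 0.8 for the preferred order). Balance on age, education, gender and the screening PHQ-9 (already collected, sections 4.1 and 6.1), with cut-points fixed in advance. Permuted blocks of varying size stratified by PHQ-9 are an acceptable alternative.
3. Conceal the next allocation from whoever enrols.
4. Report baseline characteristics by order descriptively, with no test acting as a trigger.
5. Adjust comparisons that depend on order for the allocation variables.

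**Cost.** Protocol wording and settings in the randomisation program; no extra patients or visits. Each option has a drawback. Minimisation is the more guessable on average, so step 3 matters, particularly as section 3.1.2 says researchers know each subject's site. Stratified blocks balance severity but leave the other three variables largely to chance. Neither method guarantees balance on variables outside the algorithm.

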7.4.2 Efficacy Analysis

Efficacy analyses will focus on comparisons between clinical symptoms at baseline, after the first 2-week treatment period, and at the end of the second 2-week treatment period. As noted above, the primary endpoint of this study will be a comparison focusing on clinical improvement due to TMS performed at either the standard brain target or the fMRI-guided brain target.

7.4.3 Interim Analysis

After the first 12 participants are run for each protocol, the study team will evaluate the overall rate of change in symptoms. If less than one quarter of participants experience at least a 25% reduction in Hamilton Depression scores, the team will consider a change in stimulation protocol or target. Safety and tolerability will also be assessed at this interval and if the team decides that the procedures are safe and appropriate, enrollment will continue up to 60 participants.

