3.2.3 Primary Safety Endpoints

Study follow-up will be conducted monthly, over a 6-month period upon completion of the study in order to determine the duration and stability of clinical improvements. In addition, a clinical assessment will be conducted at the end of each 2-week administration of TMS to any changes in mood and/or symptoms across the study as it is completed.

4 Study Population and Duration of Participation

We plan to enroll 80 patients to obtain useable data from 40 patients diagnosed with PTSD or trauma induced MDD and symptoms of depression, as determined by meeting the DSM criteria for PTSD or trauma induced MDD and having a PHQ-9 score \geq 10, will be recruited for this study. Participants will be otherwise healthy, aged 18-60, without significant concomitant diagnoses.

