4.3 Subject Recruitment

All participants will be recruited through the University of Pennsylvania, the Veterans Administration Medical Center, and surrounding community to find 80 patients with PTSD and trauma induced MDD and depressive symptoms. All subjects will express interest by initiating contact with the research staff or by confirming with their referring physician that they wish to be contacted for a screening procedure. All subjects fitting inclusion criteria will be approached by study staff to continue in the study. Additional recruitment methods will include Penn media services, social media, online advertisements (e.g. Craigslist), and fliers to be posted in the local community.

This study will also utilize Facebook as a recruitment resource. The CNDS Lab account will list posts on its page twice a week advertising for this specific study. This account is managed by [name].

In order to facilitate the enrollment of interested subjects in multiple studies, center-wide general prescreening forms phone screen and self-report screen will be used. Because the Center for Neuromodulation in Depression and Stress has numerous studies that are all closely related, in both purpose and eligibility criteria, a general pre-screening (both phone and self-report) has been created. Many participants will be eligible for multiple studies and will be presented the opportunity to participate in all studies that they are eligible for. An additional benefit of a shared or general pre-screening is that participants who do not qualify for a specific study can be informed of other studies they are eligible for. It will be clearly explained to all individuals that this pre-screening is for multiple studies and that their information will be stored in REDCap.

Since approval of v1.0, the center-wide prescreening has successfully increased enrollment of eligible participants across studies as well as significantly reduced burden on interested participants and study staff. The proposed modification (Sept. 2019) to the screening form (v3.4) will update eligibility criteria to be more reflective of current protocols and reduce participant response burden by optimizing branching logic, clarifying language, and implementing standard symptom severity scales. This modification (v3.4) will not be available to potential participants until all actively enrolling CNDS studies obtain IRB approval. Until

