6.7 Safety Evaluations

Only individuals trained by the Principle Investigator ([name].) and Center Director ([name].) will dispense TMS. The licensed physician ([name] or a suitable medically trained stand-in) will closely supervise any medical instability in patients and will specifically be responsible for training and overseeing syncope and seizure management which are not expected given our screening process but are the two primary health risks with TMS treatment.

[name], a board certified physician, will review all questionable screens for MRI and TMS safety and will be physically present (or a reasonable medically trained stand-in) for every TMS session conducted on any participant who indicates greater than minimal risk for experiencing syncope or a seizure in response to TMS.

Only research personnel will have keys and access to the TMS devices.

7 Statistical Plan

All recruitment will be conducted through the University of Pennsylvania, the Veterans Administration Medical Center, and surrounding community to find 80 patients with PTSD or trauma induced MDD and depressive symptoms. It is anticipated that a large portion of individuals will screen fail, withdrawal from participation or have unusable data. Therefore, 80 individuals will be consented/enrolled in this study, to ensure that there are 40 patients who complete the full protocol with usable data. This sample should provide us with adequate data to compare treatment sites relative to one another, since all patients will receive the standard targeting for TMS and also fMRI-guided TMS.

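### Section 7.4.3 lets enrolment run only to 60, while the summary and sections 4, 4.3, 4.5 and 7 plan 80; if both count consented people, 60 gives about 30 evaluable patients, not 40

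*Combined protocol and SAP*

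**What the plan says.** Section 7.4.3 (Interim Analysis) sets a look at symptom change and safety, timed as follows: "After the first 12 participants are run for each protocol". If the team finds the procedures safe and appropriate, "enrollment will continue up to 60 participants".

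The other places that bear on the number of patients are:

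- Study summary: N of 80 and n of 40.
- Section 4: "We plan to enroll 80 patients to obtain useable data from 40 patients".
- Section 4.3: recruitment through the university, the veterans' hospital and "surrounding community to find 80 patients with PTSD and trauma induced MDD and depressive symptoms". No evaluable number is given here.
- Section 4.5: "approximately 80 subjects will be consented/enrolled at Penn in order to produce 40 evaluable subjects in total".
- Section 7, opening paragraph: "80 individuals will be consented/enrolled in this study, to ensure that there are 40 patients who complete the full protocol with usable data". The reason given is that "a large portion of individuals will screen fail, withdrawal from participation or have unusable data".
- Section 3.1: 40 patients are to be recruited; 80 is not mentioned.
- Section 7.3: a power calculation that arrives at a minimum of 6 patients.

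**The concern.** Section 7.4.3 is the only place that says how far enrolment goes once the interim look has been passed, and its number disagrees with the total planned in five other places. Section 7 rests the adequacy of the site comparison on having 40 completers with usable data, and it expects heavy losses on the way from 80 to 40. A team that follows section 7.4.3 literally would stop 20 people earlier than the rest of the plan assumes. At stake is whether the evaluable sample that the plan promises is the one that its continuation rule delivers.

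**Working it through.** **Inputs.** Planned enrolment is 80 and the evaluable target is 40 (summary, sections 4, 4.5 and 7). The limit after the interim look is 60 (section 7.4.3). The plan states no loss rate, so the rate is back-derived from its own two totals.

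**Step 1: the plan's own figure.** Implied yield = 40 / 80 = 0.50, so implied loss = 1 - 0.50 = 0.50. Enrolment needed = 40 / (1 - 0.50) = 80. This matches the plan. Because the 50% comes from the same two numbers, it is a consistency check and not an independent derivation of 80.

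**Step 2: the yield at 60.** If the 60 is counted in the same unit as the 80, evaluable = 60 x 0.50 = 30. The shortfall is 40 - 30 = 10, and 10 / 40 = 25%.

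**Step 3: the range.** The yield is uncertain, so other assumed values at 60 enrolled are:

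- 40%: 60 x 0.40 = 24
- 50%: 60 x 0.50 = 30
- 60%: 60 x 0.60 = 36
- yield needed for 40: 40 / 60 = 66.7%, that is, a loss of no more than 33.3%

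**Step 4: what 30 instead of 40 could mean (illustration only).** The plan gives no effect size or power for the difference between sites. Assume a paired t test on the within-patient site difference, two-sided 0.05, with 80% power. The detectable standardised difference d solves P(T > t[0.975, n-1]) = 0.80, where T is noncentral t with n - 1 degrees of freedom and noncentrality d x sqrt(n).

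- n = 40: d = 0.454
- n = 30: d = 0.529

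**Step 5: does another passage support 60?** Section 3.1 gives 40, which agrees with the evaluable target. Section 7.3 gives a minimum of 6 for a change in symptoms. Neither leads to 60.

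**The case against.** The strongest objection concerns the counting unit. Sections 4.5 and 7 count the 80 as consented or enrolled, and section 7 places screen failures inside it. Section 7.4.3 times its look by participants run and then speaks of enrolment up to 60 participants, without saying whether these are consented, randomised or treated. If the 60 means people who have already passed screening, the 50% yield does not apply and 40 evaluable could be reached. The documents do not divide the 50% loss between screen failure, withdrawal and unusable data, so this cannot be settled. The objection stands: the word enrolment favours the same unit as the 80, but the figure of 30 is conditional.

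It can also be said that 40 was never derived from a power calculation. The only one in the plan asks for 6, and neither 30 nor 40 falls below that. This is true, but that calculation concerns change in symptoms, whereas the primary objective in section 2.1 is to compare the two sites. It does not make the discrepancy harmless.

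Three stronger readings go beyond the documents:

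- A reader might infer that every other section requires 80. Section 3.1 says 40 recruited, section 7.3 says at least 6, and section 4.3 gives 80 with no evaluable number.
- A reader might infer that power drops from 80% to 67%. That figure is arithmetically right at a difference of 0.454, but 0.454 is the value solved to give exactly 80% with 40 patients. The plan states no such target, and its primary analysis is a Site x Time ANOVA.
- A reader might infer that the team would choose between 60 and 80 after seeing results. Section 7.4.3 looks at the overall rate of symptom change and describes no site comparison. Its efficacy trigger leads to considering a change of stimulation protocol or target, and the sentence with the 60 turns on safety and appropriateness. Section 3.1.2 says that the researchers know the stimulation site, so two totals leave an opening, but nothing shows that such a choice is intended.

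**Conclusion.** The discrepancy is real and should be corrected: 60 in section 7.4.3 against 80 in the summary and sections 4, 4.3, 4.5 and 7, with no explanation of the 60. It is an inconsistency between sections and not an error in a stated calculation, but it lies inside a decision rule, so it is more than clerical.

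Its size depends on one assumption, that the 60 counts consented or enrolled people as the 80 does. Under that assumption the plan's implied yield gives about 30 evaluable patients, 10 below target. The shortfall remains at every assumed yield up to 60% and closes only at 66.7%. The loss of precision (0.45 to 0.53 in standardised units) shows scale only, because the paired test, its sidedness and its power are all assumed. The conflict between 60 and 80 is certain; the figure of 30 is not.

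**What to change.** In section 7.4.3, replace 60 with the 80 consented or enrolled used in the other sections, and state the counting unit: consented, randomised or treated.

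If 60 is the intended cap on consented or enrolled people, keep it. Then restate the enrolment total as 60 and the evaluable target as about 30 in the summary and sections 4, 4.5 and 7, and change the recruitment total in section 4.3 to 60.

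In either case, reword section 3.1 so that 40 is the evaluable number and not the number recruited, or give the revised target there if it changes.

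The first option costs one number, a short definition and one rewording, with no enrolment beyond what the other sections already plan. The second changes text in more places and accepts a smaller evaluable sample than the one section 7 calls adequate, so that statement would need to be revisited.
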